The overall study uses a stepped-wedge design to understand PrEP implementation at eight study sites in Yunnan, China. Each study site will go through four study periods. Sites will start with a six-month pre-baseline period, where PrEP is not offered but HIV prevention utilization data will be collected among MSM client population. HIV prevention utilization data will be captured by the PrEP M&E data system created by Yunnan CDC. Examples of indicators to be collected include number and frequency of HIV and STI tests, diagnoses, and treatment status. These metrics will be collected throughout all study periods. Each site will then have a different length of Baseline Period of standard PrEP implementation followed by a one-year Experiment Period with enhanced PrEP implementation.

The study procedures involve audio recording of research subjects. All study procedures will be performed at eight study sites by research staff who have completed human subject protection training after obtaining informed consent from participants. This study will not use previously collected biospecimens, data or records. Detailed study procedures are listed below:

Audio and/or video recording of research subjects: This study will conduct in-depth interviews with (1) MSM clients, and (2) program staff to understand their experience with PrEP implementation. Interview guides are submitted in English only as these are documents to guide the English-Chinese bilingual interviewers. Therefore, no Chinese version of the interview guide is attached. We will audio-record interviews with participants who provide permission for recording. Audio-recording is a very widely used technique in qualitative research. It allows researchers to fully engage and concentrate on the interview rather than writing notes, which may be a distraction for both the

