interviewer and the participants. Audio-recording will help researchers keep accurate records of qualitative data and capture non-verbal expressions during the interview. Informed consent will be obtained before any study procedures are initiated. During the consent process, the interviewer will ask participant's permission for audio-recording. For detailed process of obtaining consent, please see section "Informed Consent Process". After informed consent is obtained, the interviewer will announce that the interview will begin and turn on audiorecording equipment. The interviewer will begin the interview by noting the time, date, and unique ID number for the interview. S/he will proceed to conduct the interview guided by the interview guides. The interview will be in-person or remotely one-on-one and is expected to last 45 to 60 minutes. All data will be confidential and protected. Compensation of 100 Yuan (approximately USD \$16) will be provided upon completion of the interview. De-identified data will be sent to contractors external to Columbia University to support data analysis.

Study Design

B-HAPPY is a multisite randomized stepped-wedge trial to compare the effectiveness of two implementation strategy bundles: 1) Standard Implementation: comprising the strategies that the Yunnan CDC would usually use to introduce HIV prevention innovations in the absence of the proposed study; and 2) Enhanced Implementation: standard implementation enhanced by a SIC-guided approach to plan and implement PrEP. Eight sites will receive identical Standard Implementation during a six-month baseline period; additional strategies will be introduced to blocks of 2 sites in six-month increments. Importantly, the role of the SIC will shift between Baseline when

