over 6 months. The study team set 80% targets for two reasons: 1) 80% targets are commonly used in observational facilitated training in implementation processes; 2) the PI's recently-published PrEP modeling analysis clearly showed the differential epidemiological impact a high real-world PrEP effectiveness would have compared to a low real world effectiveness: with 80% effectiveness, PrEP would lead to 345,000 infections averted over a 20-year horizon compared to 219,000 with 50% effectiveness and 87,900 with 20% effectiveness (Zhang et al., 2018), spurring the team to choose ambitious targets that could drive down infections among MSM. To examine the implementation process and efficiency of the Enhanced versus Standard implementation approaches we will use SIC and COINS tools to monitor sites for implementation process and resource use. Outcomes will include proportion of implementation activities completed, duration of each implementation phase, and cost and resource allocation for completion of each implementation phase (Aim 2). Based on robust studies that assess implementation using the SIC, *we hypothesize that time and resources spent in Pre-Implementation will be associated with higher odds of successful implementation and sustainment.*

Recruitment

All recruitment activities will take place at our international site (Yunnan, China) and will be conducted in Mandarin Chinese, the primary language of the region, by Chinese-speaking research staff. All research staff will complete the required human subject training before conducting any recruitment activities. All procedures related to recruitment have been reviewed and approved by Yunnan CDC IRB. Columbia personnel will not be involved in the recruitment of participants.

Two types of participants will be recruited for in-depth interviews in our study: (1) MSM clients of participating facilities; (2) program staff who are involved in PrEP implementation. We will conduct the interviews with clients and program staff in each study period, as a result, a total of four rounds of interviews will be conducted.

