Model building, estimation, and significance testing. The nested data structures will be evaluated using mixed-effects regression models, but with 8 sites, specialized methods are required to estimate and validate the effects.^{29,30} Model estimation will utilize Bayesian Markov chain Monte Carlo (MCMC) methods.²⁷ With this approach, the results are based on a large number of replications, providing an empirically-based sampling distribution—rather than a single point estimate—for each model parameter (e.g., the effect of Enhanced Implementation). Further, the conclusions will be validated using a frequentist, fixed effects approach (i.e., dummy-coded indicators) to control for site effects.³¹ To test for within-block changes across the three periods, two dummy-coded indicators will be included to differentiate the Enhanced and Observation periods from the reference Standard period. Continuous, dichotomous, and ordered categorical outcomes will be evaluated according to Gaussian, binomial, and ordinal distributions. To evaluate the magnitude and precision of effects, 95% CIs will be computed, along with odds ratios (ORs) for non-linear outcomes. The Bayesian MCMC models will be implemented in MLwiN,²⁷ and single-level regression models will be implemented in R.³²

Evaluation of Specific Aim 1: To evaluate whether the addition of SIC-guided PrEP delivery (Enhanced Implementation) to standard health system PrEP delivery improves services outcomes, including: awareness, screening, offer, initiation, and continuation at 6 months. Although the outcomes are repeatedly monitored, each reflects a client-level status. The three-level mixed-effects regression model, with clients (level-1) within periods (level-2) within sites (level-3), will include control variables for client characteristics (e.g. age, partnership status, ethnicity [Han vs other], sexual identity) and site characteristics (e.g. staffing, collaboration history between VCT and

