Implementation outcomes. For Aim 2, with the focus on implementation process outcomes (rather than client services outcomes), the data are structured with three periods (level-1) within sites (level-2). The outcomes include the proportion of implementation activities completed, duration of activity completion, maximum implementation stage reached, and benchmarks on the Five-80s (3 consecutive months for implementation, 6 consecutive months for sustainment). The model will include key client and site characteristics, and dummy-coded indicators to differentiate the three periods. The results will indicate the difference between Enhanced and Standard in the level of each implementation outcome. As with Aim 1, the conclusions will be validated based on single-level models with fixed-effect control variables for site differences. Likewise, with the focus on achieving implementation process benchmarks, the model

will be extended to a time-to-event framework,²⁹ testing for differences between Enhanced and Standard in the time required to achieve benchmarks (adjusted for the duration of the Standard period). With the focus on implementation process outcomes, power for this aim is inherently limited. Results will focus on estimates of 95% CIs for the effect of Enhanced Implementation.

Attrition & Missing Data. Following intention-to-treat principles, sites will be retained in research measurement independently of participation in Enhanced Implementation.³⁴ Highly successful tracking and retention protocols will minimize missing data. However, some data will inevitably be missing. To address this, assumptions will be evaluated, and informed by the results, one of several approaches will be used³⁵: i) For a small proportion of missing data with evidence of Missing at Random (MAR), the data will be analyzed using the estimation procedures described above. ii) For a non-trivial amount of missing data and evidence of MAR, multiple imputation for repeated measurements will be used.³⁶ iii) For a non-random missing data mechanism, pattern mixture models will be used to identify and control the effect of the non-random mechanism.^{37, 38}

Data Analysis

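### Aim 2 compares SIC activity and phase durations across periods of unequal length, with no censoring rule for work unfinished at period end

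*Combined protocol and SAP*

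**What the plan says.** Time is one of the three things Aim 2 compares, and the Study Design section lists phase duration among its outcomes. In the Statistical Analysis Plan, the paragraph on implementation outcomes sets up three periods within each site and states: "The outcomes include the proportion of implementation activities completed, duration of activity completion, maximum implementation stage reached". It then says: "The results will indicate the difference between Enhanced and Standard in the level of each implementation outcome".

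The paragraph on model building gives the distributions: "Continuous, dichotomous, and ordered categorical outcomes will be evaluated according to Gaussian, binomial, and ordinal distributions". Duration is not named there. A Gaussian model follows only by inference, because duration is continuous and no other model is offered for a continuous level.

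On window lengths, Study Design says "Eight sites will receive identical Standard Implementation during a six-month baseline period" and "additional strategies will be introduced to blocks of 2 sites in six-month increments". Study Procedures says "Each site will then have a different length of Baseline Period of standard PrEP implementation followed by a one-year Experiment Period".

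The SIC data description (Confidentiality of study data) is a log of completed activities with their completion dates. No section says what duration is recorded for an activity or phase still open when a period ends.

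The implementation-outcomes paragraph does extend the model to a time-to-event framework, adjusted for the length of the Standard period. That extension is stated for the time needed to reach benchmarks. The same paragraph uses that word for the Five-80s and lists it separately from duration.

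**The concern.** A duration is observed in full only if the work finishes inside the window. Otherwise it is known only to exceed the window, and the window is set by the randomised step schedule. Two scoring rules suggest themselves, and neither is neutral. Keeping only finished durations selects the fast ones, more severely in a short window than in a long one. Setting unfinished durations to the period end writes the window length into the outcome.

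Site fixed effects do not remove this, because the window changes within a site between Standard and Enhanced. The result could be a false time difference where none exists, or a real saving shown too small. The Aim 2 cost analysis also uses SIC duration scores as covariates in the model for sustainment, so the scoring choice carries forward.

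**Working it through.** **No plan figure to reproduce.** The documents give no expected duration, effect size or power figure for Aim 2.

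**Windows.** 8 sites in blocks of 2 make 4 blocks. A first Standard window of 6 months and 6-month steps give Standard windows of 6, 12, 18 and 24 months. Enhanced is 12 months at every site.

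**Is cut-off realistic?** One example in the SIC data description is the first client kept in PrEP care for six months. In the first block's 6-month Standard window, that can be reached only if a client starts at the very beginning.

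**Assumption.** Completion time T is gamma with shape 1 to 3 and a mean of 3 to 18 months. S(t) is the probability of being unfinished at t, and c is the window.

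- Finished only: E[T | T < c] = (∫₀ᶜ S(t)dt − c·S(c)) / (1 − S(c))
- Set to period end: E[min(T, c)] = ∫₀ᶜ S(t)dt
- Expected estimate: Enhanced value at c = 12, minus the mean of the Standard values at c = 6, 12, 18, 24 (sites weighted equally)

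**One case in full: shape 1 (exponential), mean 12 in both periods, no true effect.**

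- Unfinished in Standard: e^(−c/12) = 61%, 37%, 22%, 14% by block; in Enhanced, 37%.
- Set to period end: Standard 4.722, 7.585, 9.322, 10.376, average 8.001; Enhanced 7.585. Difference 7.585 − 8.001 = −0.42 months.
- Finished only: Standard 2.75, 5.02, 6.83, 8.24, average 5.71; Enhanced 5.02. Difference −0.69 months.
- By block, finished only: +2.27, 0, −1.81, −3.23. Large errors of opposite sign partly cancel in the average.

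If the Enhanced mean is truly 6 (a saving of 6 months), the Enhanced values become 5.19 (set to end) and 4.12 (finished only). The saving then appears as 2.81 or 1.59 months.

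**All cases, shapes 1-3, both rules, in months.**

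| True means, Standard → Enhanced | True saving | Estimate |
|---|---|---|
| 3 → 3 | 0 | Enhanced 0.0-0.1 slower |
| 6 → 6 | 0 | −0.2 to +0.2 |
| 12 → 12 and 18 → 18 | 0 | Enhanced 0.1-1.2 faster |
| 3 → 2 | 1 | saving 0.7-1.0 |
| 6 → 3 | 3 | saving 1.5-2.6 |
| 12 → 6 | 6 | saving 1.6-3.6 |
| 18 → 12 | 6 | saving 1.3-2.3 |

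Weibull times (shape 2) agree: the 12 → 6 saving appears as 2.5 (finished only) or 3.6 (set to end). Weighting finished durations by the chance of finishing, instead of equally, raises the null error at means of 12-18 to 1.2-3.2 months and shows the 18 → 12 saving as 2.0-3.8.

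**Check of the remedy.** The estimate is the ratio of completions per month at risk, Enhanced to Standard, censored at period end. It was simulated with exponential times, 8 sites, 20 activities per site and 4,000 replicates. The mean log ratio was about 0.00 with no effect, and 0.69-0.70 when the Enhanced mean was half the Standard mean (truth ln 2 = 0.693).

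**Check of an alternative.** For 18 → 12, the restricted mean difference is 1.2-1.4 months over a 12-month horizon and 0.2-0.4 over 6 months. It removes the false null difference but does not recover the 6-month saving.

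**The case against.** A reader might infer that the Aim 2 time comparison is biased as it stands. The documents do not support that as a certainty. They give no scoring rule, so both rules above are assumptions, and the SIC duration score may have its own rule that is not reproduced here. For work averaging about 3 months, almost everything finishes inside the window and the distortion is negligible. For the same reason, it cannot be said in general that most of a real saving is hidden; that depends on long durations. The large block-level errors are not the planned estimate, which averages over sites. These limits stand.

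A reader might also infer that the plan ignores unequal period lengths. It does not: the time-to-event extension adjusts for the length of Standard. If benchmarks were read broadly to include SIC milestones, part of the gap would close, but the paragraph ties the word to the Five-80s and lists duration apart from it. Other time-to-event analyses are described only as supplementary and possible. Pattern mixture models are offered for non-random missingness, but the plan does not link them to unfinished work, and a known period end is handled more directly by censoring.

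The proportion completed and the highest stage reached are analysed alongside, so unfinished work is not invisible. They do not correct the duration estimate. Limited power for this aim, which the plan admits, is a reason to interpret intervals cautiously; it does not make a distorted centre acceptable.

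**Conclusion.** The point holds in a conditional form. Durations are compared as levels over windows that differ by design, no censoring rule covers them, and the one method in the plan that would handle this is stated for another outcome. Where a material share of work is unfinished at period end, either natural scoring rule distorts the within-site contrast.

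The size depends on how long the work takes. It is trivial at a mean of about 3 months. At means of 12-18 months there is a false advantage of up to 1.2 months for Enhanced, and a true 6-month saving is shown as 1.3-3.6 months. These figures rest on assumed gamma times, equal site weights and the windows derived above. The Gaussian model is inferred, but the distortion comes from the handling of unfinished work, not from the choice of distribution. The change should be made before the Aim 2 duration analysis.

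**What to change.** Extend the planned time-to-event model to SIC activity and phase durations. Measure time from the start of each period (or of the activity or phase, stating which), censor at period end, and include a site effect. Report the Enhanced versus Standard event-rate or hazard ratio with its 95% CI as the main time result, in place of the difference in mean duration. A restricted mean difference over a common horizon may be added as a description, with a statement that it captures only the time saved within that horizon.

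The cost is SAP wording: the log already dates completions, and the plan already names the method. The drawbacks are wider intervals and a ratio that relies on a proportional-rate assumption, which 8 sites can test only weakly. The simulation supporting the ratio used exponential times and no variation between sites.

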it will be used as an observational assessment tool only, and Enhanced, when it will be used both to guide implementation and to assess it. During Enhanced Implementation each site will receive Implementation Support to plan and introduce PrEP by following the eight stages of the PrEP-adapted SIC. Implementation Support will involve a centralized TA system developed using US-based PrEP experience. The support will utilize a **SIC-guided systems analysis and improvement approach** that focuses on addressing implementation issues identified through real-time analysis of client, provider/site, and implementation data. During the study, sites will participate in four study periods: a Pre-Baseline Period (Routine service with no PrEP implementation), a Baseline Period (Standard Implementation of PrEP), an Experiment Period (Enhanced Implementation of PrEP), and a Post-Experiment-Sustainment Period. Sites are randomized to the *timing* of the intervention phase—the intervention condition changes over time and the intervention effect is the difference in outcomes between the Baseline and Experiment Periods, and the Post-Experiment and Baseline Periods.

We hypothesize that adding SIC-guided implementation onto standard health system implementation of PrEP will improve outcomes and lead to greater likelihood of a) implementation success and b) sustainment. Successful implementation will be defined as a site achieving "Five-80%" targets and maintaining them three months in a row (Aim 1): 1) *Awareness of PrEP among 80% of MSM clients*; 2) *PrEP eligibility assessment for 80% of MSM clients*; 3) *PrEP linkage for 80% of MSM clients who wish to start and are medically-eligible*; 4) *PrEP initiation for 80% of MSM who are linked to PrEP services*; and 5) *six-month PrEP continuation for 80% of those who remain PrEP-eligible*. Sustainment will be defined as achieving the Five-80% targets continuously

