All data will be in electronic format and we will not have any hard copy of study data. In general, we will use Secure Sockets Layer (SSL) encryption to securely transfer the study data that are in electronic format. We will store study data on password-protected, encrypted computers, and will restrict access to the data to key study personnel.

This study will analyze data from five different sources. Here is a detailed description of how we will ensure confidentiality and safely stored data from five different sources:

1. SIC and COINS data

Description: The PrEP-SIC data includes a log of implementation activities completed by each site along with the dates of activity completion (e.g.: date written PrEP implementation plan completed, date first PrEP user retained in care for six months). The COINS tool assesses direct and indirect expenses, including the number of hours per role expected in completing each implementation activity listed in the SIC. SIC and COINS data will be collected by our Yunnan-based research coordinator through phone call and in-person site visits at two to four-week intervals and entered

into the SIC website. SIC and COINS tool measures implementation process and does NOT contain personal identifiable information (PII) or protected health information (PHI).

2. PrEP M&E data

Description: Yunnan CDC (our primary collaborator in China and a subaward recipient on this grant) is upgrading their HIV prevention monitoring and evaluation (M&E) system to incorporate PrEP service delivery indicators. We expect this PrEP M&E data system to start working in May 2020, and it will document data including routine HIV utilization, PrEP service delivery and process measures for all facilities involved in PrEP implementation across the province and including at our study site. Yunnan CDC staff will extract data and aggregated at site level (e.g. number of HIV testing done per site, percentage of MSM clients receiving sexual health needs assessment, number of PrEP initiations). Only this site-level, aggregated data will be shared with the B-HAPPY study team.

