Traditional designs—whether client-randomized or site-randomized—were not viable due to statistical power, contamination risk, and the dual focus on intervention and implementation outcomes. For instance, randomizing clients would risk contamination within sites, and randomizing sites would drastically restrict power. This

is addressed by the proposed stepped-wedge design,²⁵⁻²⁷ with all sites participating in a baseline period (Standard Implementation), experiment period (Enhanced Implementation), and post-experiment period (Observation). Blocks of sites are randomized to the *timing* of the experiment period. Because intervention condition *changes over time*, the intervention effects reflect within-block changes (e.g., between the Enhanced and Standard periods). The design is highly flexible and maximizes power, and the proposed analyses straightforwardly accommodate different data structures for client-services outcomes (Aim 1) and implementation process outcomes (Aim 2), clients that span periods, and outcomes that are both research- and site-collected.

Data structure. For Aim 1, the *client-services outcomes* are structured with repeated visits (level-1) that are nested within clients (level-2) who are nested within periods (level-3) that are nested within sites (level-4). However, for analysis, the outcomes will reflect a single status for each client (e.g., initiation of PrEP), reducing the data to a three-level structure. For Aim 2, the *implementation process outcomes* are structured with three repeated measurements (i.e., across the baseline, enhanced, and observation periods; level-1) that are nested within sites (level-2). In each case, the small number of sites will be addressed. Of note, across aims, supplementary time-to-event analyses^{28, 29} (e.g., the effect of Standard Implementation on time to client awareness) are possible by reformulating the data to client- and site-period structures. Likewise, clients will be associated with the period in which the outcome status is finalized.

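### A site with six months of Standard cannot reach either Five-80% benchmark, and the Aim 2 level comparison has no rule for such site-periods

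*Combined protocol and SAP*

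**What the plan says.** **Schedule.** Study Procedures gives each site six months without PrEP, then Standard for a length that differs by site, then one year of Enhanced. Study Design gives all eight sites a six-month baseline, after which blocks of two sites step at six-month intervals. No table of step dates is printed.

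**Benchmarks.** Success means meeting all five targets for three consecutive months; sustainment means six. The fifth target is "six-month PrEP continuation for 80% of those who remain PrEP-eligible". Study Design ties success to the first aim ("maintaining them three months in a row (Aim 1"), but the SAP analyses it under Aim 2, where the outcomes include "benchmarks on the Five-80s (3 consecutive months for implementation, 6 consecutive months for sustainment".

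**Analysis.** In the Implementation outcomes section, period indicators are fitted and checked with site fixed effects: "The results will indicate the difference between Enhanced and Standard in the level of each implementation outcome". A time-to-event extension follows, "testing for differences between Enhanced and Standard in the time required to achieve benchmarks (adjusted for the duration of the Standard period". No time origin is given.

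**Crediting.** The Data structure section says "clients will be associated with the period in which the outcome status is finalized". This is written for clients, not for site-level rates.

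No section says how to score a site-period in which the fifth target cannot yet be measured. The missing-data text does not cover it.

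**The concern.** The trial's stated hypothesis is that Enhanced makes implementation success and sustainment more likely. Nobody can have six months of PrEP until about six months into Standard, so early-stepping sites have little or no Standard time in which either benchmark could be met. Continuation among Standard starters is already maturing when Enhanced begins, so Enhanced does not carry the same handicap. Unless the analysis allows for this, part of the Enhanced-versus-Standard contrast is set by the calendar. The section concedes limited power and relies on 95% confidence intervals, but an interval centred on a shifted value misleads whatever its width.

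**Working it through.** The plan gives no figure of its own to reproduce here.

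**1. Earliest possible months.** Let m be the first Standard month with a six-month continuation reading, assuming a first initiation on day 1. Then m = 6 if month 6 itself counts, and m = 7 if six full months must have passed.
- Earliest success: m + 2 = month 8 or 9.
- Earliest sustainment: m + 5 = month 11 or 12.

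**2. Room in each block.** Study Design gives L = 6 months for block 1. The lengths 12, 18 and 24 are the natural reading of six-month steps but are not printed. Measurable months = L − m + 1; slack = L minus the earliest month. Entries are for m = 6 / m = 7.

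| Block (2 sites) | L | Measurable months | Slack, success | Slack, sustainment |
|---|---|---|---|---|
| 1 | 6 | 1 / 0 | −2 / −3 | −5 / −6 |
| 2 | 12 | 7 / 6 | +4 / +3 | +1 / 0 |
| 3 | 18 | 13 / 12 | +10 / +9 | +7 / +6 |
| 4 | 24 | 19 / 18 | +16 / +15 | +13 / +12 |

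Every site has 12 measurable Enhanced months if continuation is credited to the period in which it is finalized.

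**3. Ceiling.** Suppose every measurable month meets all five targets in both periods, and an unreachable site-period counts as a failure. Standard reaches 6/8 = 75% and Enhanced 8/8 = 100%, a gap of 25 points. If only one site had a six-month Standard period and all others could reach the benchmark, the gap would be 8/8 − 7/8 = 12.5 points.

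**4. Below the ceiling.** Assume the same monthly chance q of meeting all five targets in both periods, independent months and m = 7. The chance f(n) of a run of k in n months follows f(n) = f(n−1) + [1 − f(n−k−1)](1−q)q^k, with f(k) = q^k and f(n) = 0 for n < k. Standard is [0 + f(6) + f(12) + f(18)]/4; Enhanced is f(12). Gaps come from unrounded values.

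| q | Success: Standard vs Enhanced, % | Gap, points | Sustainment: Standard vs Enhanced, % | Gap, points |
|---|---|---|---|---|
| 0.3 | 13.9 vs 18.9 | 5 | 0.3 vs 0.4 | 0.1 |
| 0.5 | 41.1 vs 58.4 | 17 | 4.6 vs 6.2 | 1.6 |
| 0.7 | 63.5 vs 91.0 | 28 | 23.6 vs 32.9 | 9 |
| 0.9 | 73.7 vs 99.9 | 26 | 58.5 vs 85.0 | 27 |

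With lag-1 autocorrelation of 0.8 the gaps are 13/20/24/25 for success and 7/13/19/24 for sustainment.

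**5. Planned adjustments, level model.** At q = 0.8 the success gap is 0.279 with or without Standard duration or site fixed effects. Duration is constant within a site, so it is collinear with the site effects.

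**6. Time-to-event, null hazard ratio (Enhanced/Standard), q = 0.3/0.5/0.7/0.9.**
- Clock restarted at each period start, adjusted for Standard duration, constant baseline hazard: success 1.87/2.11/2.67/3.63, sustainment 1.84/1.85/1.93/2.26. Month-specific hazards on this clock give larger ratios (at least 2.77 and 3.78).
- One clock from the start of Standard, month-specific hazard, time-varying Enhanced indicator, runs allowed to cross the step: 1.00 throughout, with or without duration.
- The same single clock, without the duration term, counting only runs inside one period: 0.89–0.97 for success and 0.65–0.82 for sustainment.
- Clock started in each period at the first month with all five targets measurable, compared by month since that start, within-period runs only: 1.00 throughout.

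**7. Check of the binary remedy.** Excluding block 1 and using equal windows of 6, 12 and 12 months in blocks 2–4 gives identical null attainment in both periods (success 15.4/49.3/82.4/98.2%, sustainment 0.3/4.7/25.9/74.4%). Excluding block 1 with unequal windows leaves up to 6.4 points for success (q = 0.7) and 7.1 for sustainment (q = 0.9).

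**The case against.** **Time-to-event.** A reader might infer that the planned time-to-event analysis is biased and that its duration adjustment fails. The documents do not support that. They give no origin, and a common stepped-wedge choice, one clock from the start of Standard, gives a null ratio of 1.00. What stands is that the result depends on a choice the plan leaves open.

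**Scoring.** A reader might also take it that the plan scores unreachable site-periods as failures. No section says so, and a rate with nobody yet assessable is undefined rather than failed. The 25-point ceiling and the gaps in step 4 depend on that scoring.

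**Direction.** The sign depends on extending the client crediting rule to sites. If only Enhanced starters counted in Enhanced, the gaps at q = 0.3/0.5/0.7/0.9 would be −5.5/−9.9/+1.7/+21.1 for success and −0.2/−3.1/−11.9/−5.3 for sustainment. That is a reason to state the rule, not to leave it open.

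**Site count.** Two of eight rests on the blocks in Study Design; Study Procedures says that each site's length differs.

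**Aim 1.** The Aim 1 outcomes include "awareness, screening, offer, initiation, and continuation at 6 months", so a reader might extend the point to continuation there and conclude that block 1 yields almost no Standard data. That does not follow, because the plan does not say when the status of a client who stops early is finalized.

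**Importance.** The SAP calls the client-services outcomes primary and concedes low power for Aim 2. This limits the consequence, but low power does not excuse a shifted estimate of the stated hypothesis.

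**Conclusion.** The concern holds for the level comparison and is worth fixing. A site with six months of Standard cannot reach either benchmark before its step; this needs only the six-month baseline, no earlier PrEP and the six-month continuation target. On steps at 6/12/18/24 months, block 2 has at most one month of slack for sustainment. A start-up lag of one to two months, for which the documents give no figure, would remove it.

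If unreachable counts as failure and continuation is credited where finalized, the ceiling is 6/8 against 8/8 with no true effect. At assumed q of 0.3 to 0.9 with independent months, the null gap is about 5–28 points for success and 0.1–27 for sustainment, in favour of Enhanced. The sustainment gap is negligible at low q unless months are correlated. Site fixed effects do not remove the gap, and the duration adjustment is stated only for the time-to-event model. That model is underspecified on its origin, not shown to be biased.

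**What to change.** In the Implementation outcomes section:

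1. **Binary contrast.** Code a site-period as not evaluable for a benchmark when it has fewer measurable months than the benchmark needs (3 or 6). At each evaluable site, use equal-length windows of measurable months in both periods. For this contrast, count only runs inside one period. Report the number of evaluable Standard sites: on the assumed schedule, at most 6 of 8 for success, and 4 to 6 of 8 for sustainment depending on start-up lag.
2. **Time-to-event contrast.** Choose one of two forms. Either use one clock from the start of Standard, with month-specific baseline hazard and a time-varying Enhanced indicator, letting runs cross the step. Or start the clock in each period at the first month with all five targets measurable, compare by month since that start, and count only within-period runs. Do not combine the single clock with the within-period rule.
3. **Crediting.** State how the client rule on finalized status applies to site-level continuation.
4. **Schedule.** Reconcile Study Procedures with Study Design on Standard lengths, and print the step dates.

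The first measurable month can be taken from data already collected: initiation counts and the SIC log, which records the "date first PrEP user retained in care for six months". The design, the data collected and the Five-80% definition are unchanged.

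The cost is fewer evaluable Standard site-periods and a wider interval. With m = 7 and no lag, equal windows drop 6 Enhanced months at each block-2 site and 6 Standard months at each block-4 site. Under the client crediting rule, continuation readings in the first six Enhanced months come from clients who started under Standard. That is the whole of block 2's Enhanced window and half of those in blocks 3 and 4, and it may dilute a real effect on continuation. Equal windows also do not remove natural improvement over time.
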